## VI. Statistical Analysis

- a) *Statistical Plan:* The Mann-Whitney U test will be used to analyze differences in changes of QEEG between responders and non-responders to CBT. We will use logistic regression with the outcome being response/no response on the HAMD-17 and the predictors being other EEG measures. We will test the predictors in a stepwise manner given the limited power with a small N. A power calculation based on a previous QEEG study conducted in our clinic reveals that, to achieve power = 0.80, we would need 34 subjects per group. With N = 30 per group (60 subjects total), our power is 0.76. Power for the current study, with N = 15 per group, is 0.47. While this study is underpowered due to the small N, the goal of this study is to act as a pilot study which can help measure effect sizes, providing a foundation for future, larger projects.

For secondary aims, we will use Pearson r's for pairs of continuous measures, or point-biserial r for pairs of dichotomous and continuous measures.

Data from the Signal Detection Fact Task will be analyzed by [name] at Harvard University. Response bias will be the main variable of interest, whereas reaction time, hit rates, and discriminability values will provide control variables. Analyses of variance (ANOVAs) will be used to investigate variables across the three blocks. Discriminability and response biases will be computed using standard formulae (e.g. McCarthy and Davidson 1981).

- b) *Study Endpoints:* Endpoints will be defined as the final study visit at the end of the 12 weeks, or the termination/final visit for patients who choose to (or have to) end participation in the study prematurely.

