Quantitative Electroencephalogram (QEEG) Predictors of Response to Psychotherapy
Versus Antidepressant Treatment in Depression

Identifiers: NCT00824044

Unique Protocol ID: 2008-P-000838

Date prepared: 12/7/2017

Summary:

A-priori expectation from prior **medication** work is a decrease in theta activity from baseline at week 1 in responders, and an increase in non-responders. Prior work showed an increase in theta activity in **placebo** responders (and little change in non-responders). (See attached manuscript that describes changes in theta Cordance over time in both placebo and medication groups. See Fig 4 on page 128.) Also, ATR is expected to be higher in medication responders than non-responders after 1 week on antidepressant.

Methods:

ATR and Power metrics were calculated from available EEGs at baseline and subsequent visits. Change in Power between baseline and subsequent visits were derived. The data were analyzed for 3 groups: Pooled, Drug-only, Drug+CBT.

In a completer analysis (not an intent to treat), independent sample t tests were used to assess the relationship between responders (greater than or equal to 50 % reduction in the primary outcome (HAMD-17 score)) and change in QEEG metrics across time.

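### The SAP reports t tests in three groups where the protocol specified a Mann-Whitney test in CBT patients plus stepwise logistic regression, and it neither explains nor labels the departure

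*SAP*

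**What the plan says.** Protocol, Section VI, a) Statistical Plan, gives two methods. The first is a rank test confined to one arm: "The Mann-Whitney U test will be used to analyze differences in changes of QEEG between responders and non-responders to CBT". The second is a prediction model: "We will use logistic regression with the outcome being response/no response on the HAMD-17 and the predictors being other EEG measures". Selection is stepwise: "We will test the predictors in a stepwise manner given the limited power with a small N". The first method answers Primary Aim 1 in Section II, which asks whether QEEG can predict response to CBT.

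The SAP is a single page headed "Date prepared: 12/7/2017". Its Methods paragraph, in the past tense, says that "independent sample t tests were used to assess the relationship between responders" and change in QEEG metrics over time. On who was compared it says: "The data were analyzed for 3 groups: Pooled, Drug-only, Drug+CBT". It mentions no Mann-Whitney test, no logistic regression, no check of distribution and no reason for a change of method.

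**The concern.** When a protocol names a test and the later plan reports a different one without comment, a reader will take the reported test as the planned one. In samples this small, a p-value close to 0.05 can fall on either side of the line depending on the test. There are several QEEG metrics and five recording times, so an unlabelled choice of test adds to the freedom already present. Two further losses go with it. The logistic regression, the protocol's only stated model for predicting response, does not appear. Nor does the contrast that Aim 1 needs, responders v non-responders within CBT, because none of the SAP's three groups is CBT alone. The protocol has no combined drug-plus-CBT arm, so the content of the third group is unclear.

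**Working it through.** **Side by side**

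| Item | Protocol, Sections II and VI | SAP, Methods |
|---|---|---|
| Test of QEEG change by response | Mann-Whitney | Independent-sample t |
| Prediction model | Stepwise logistic regression | None named |
| Patients compared | CBT arm | Pooled; Drug-only; Drug+CBT |
| Reason for change | – | None given |

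**The plan's own power figures.** The protocol states 34 per group for power 0.80, 0.76 at 30 per group and 0.47 at 15 per group, but no effect size. I assume alpha 0.05 two-sided and use n = 2(1.960 + 0.842)²/d² and power = Φ(d√(n/2) − 1.960).
- d = 0.689: n = 15.70/0.4747 = 33.07, rounded up to 34.
- n = 30: Φ(0.689 × 3.873 − 1.960) = Φ(0.709) = 0.76.
- n = 15: Φ(0.689 × 2.739 − 1.960) = Φ(−0.073) = 0.47.

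All three figures reproduce, so a shift of 0.69 SD is a fair reading of the effect the protocol had in mind. The larger shift of 1.2 SD used below is my assumption.

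**Group sizes.** Thirty patients randomised 1:1 give 15 in the CBT arm. The documents give no response rate, so I assume a split of 7 v 8.

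**Exact size of Mann-Whitney at 7 v 8.** There are C(15,7) = 6,435 allocations. U ≤ 10 covers 129 of them, so the two-sided size is 2 × 129/6,435 = 0.040. U ≤ 11 would give 2 × 174/6,435 = 0.054, which is too large.

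**Disagreement, normal data** (60,000 simulated datasets per row, two-sided 0.05; simulation error about 0.1 point near 6%):

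| Shift (SD) | t power | Mann-Whitney power | Opposite decisions |
|---|---|---|---|
| 0 | 0.050 | 0.041 (exact 0.040) | 2.0% |
| 0.69 | 0.233 | 0.196 | 6.1% |
| 1.2 | 0.575 | 0.509 | 9.3% |

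Repeat runs put the last figure at up to 9.5%. At 0.69 SD, 24.5% of datasets are significant by at least one test, and in 6.1/24.5 = 25% of those the other test disagrees. The t test gains 3.7 points of power at 0.69 SD and 6.6 at 1.2 SD.

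**Disagreement, skewed data.** The log-normal shape is an assumption. The answer depends on whether the shift is set on the log scale or in SDs of the raw values (here applied to the group of 7):

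| Log SD | Shift | Log-scale shift: t v Mann-Whitney power; opposite | Raw-SD shift: t v Mann-Whitney power; opposite |
|---|---|---|---|
| 0.6 | 0.69 | 0.204 v 0.196; 8.0% | 0.309 v 0.329; 9.7% |
| 0.6 | 1.2 | 0.505 v 0.506; 12.9% | 0.653 v 0.688; 11.6% |
| 0.9 | 0.69 | 0.168 v 0.195; 9.7% | 0.414 v 0.517; 15.7% |
| 0.9 | 1.2 | 0.423 v 0.511; 18.1% | 0.727 v 0.802; 13.3% |

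The range is roughly 8 to 18%. Putting the log-scale shift in the group of 8 widens it to 7.5 to 20.6%.

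**Type I error if either test counts:** 0.051 to 0.055 across the normal and skewed cases.

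**The case against.** The strongest reply is that little harm follows. Which test is better is open: with normal data the t test has more power, and neither document gives a distribution for QEEG change. Log-normal values are all positive, whereas the SAP expects decreases in some patients and increases in others, so the skewed cases are only illustrations. Even taking the better of the two tests barely moves the type I error. The protocol also calls the study an underpowered pilot meant to measure effect sizes, so crossing 0.05 matters less than in a confirmatory trial. All of this stands, and it limits the point to traceability and disagreement between tests.

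It is also true that the protocol's Mann-Whitney test covers only CBT patients. For the drug-only and pooled comparisons no rank test had been named, so the SAP replaced nothing there. That narrows the substitution, but it makes the missing CBT-only contrast more important.

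A reader might infer from the date and the past tense that the t test was picked because of its result. The documents do not support that. They suggest the SAP was written late and say nothing of how the test was chosen. A reader might also speak of a changed primary test, but neither document gives any test that label.

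Finally, rewriting a 2017 account of finished analyses as though it had always named Mann-Whitney would itself mislead. The remedy has to be an open statement of departure.

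**Conclusion.** The point holds as an unexplained and unlabelled departure from the protocol's methods: a different test, no logistic regression, and no CBT-only group among those analysed. It does not show results-driven choice, and it does not show that the t test is invalid or that the rank test is superior for these metrics.

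At 7 v 8, the choice of test changes the p<0.05 decision in about 2% of datasets with no effect and 6 to 9.5% at 0.69 to 1.2 SD with normal data. It is roughly 8 to 18% if the changes are skewed. These figures rest on an assumed even split, an effect solved back from the protocol's power statement, and assumed distributions. The error-rate cost is small. The change should be made because it is cheap and removes a free choice of test, but it would not by itself overturn the study.

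**What to change.** In a dated revision of the SAP:

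- Report the Mann-Whitney test of QEEG change in the CBT arm as the pre-specified Aim 1 analysis, with exact p and the Hodges-Lehmann difference with its 95% CI. Show the t test beside it as a sensitivity analysis.
- Say which patients the Drug+CBT group contains, and give results for CBT patients alone.
- Report the logistic regression named in the protocol. The protocol's version is stepwise. If it is cut to one predictor because of the small N, label that as a change.
- State the departure from the protocol and its reason, and mark each analysis that appears only in the SAP as *not pre-specified in the protocol*.
- For the re-run, state the response cut-off and the population. The protocol uses more than 50% change and counts the termination visit as an endpoint; the SAP uses at least 50% and completers.

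The cost is SAP wording and a re-run on existing data. The downside is about 4 to 7 points less power for Mann-Whitney than for the t test if the changes are truly normal.
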